5.1.3.2 Relationship

The investigator must assign a relationship of each AE to the receipt of the investigational product. The investigator will use clinical judgment in conjunction with the assessment of a plausible biologic mechanism, a temporal relationship between the onset of the event in relation to receipt of the investigational product, and identification of possible alternate etiologies including underlying disease, concurrent illness, or concomitant medications. The following guidelines should be used by investigators to assess the relationship of an AE to study product administration. **ONLY A PHYSICIAN CAN MAKE THIS DETERMINATION.**

Not related: No relationship to investigational product. Applies to those events for which evidence exists that there is an alternate etiology.

Unlikely: Likely unrelated to the investigational product. Likely to be related to factors other than investigational product but cannot be ruled out with certainty.

Possible: An association between the event and the administration of investigational product cannot be ruled out. There is a reasonable temporal association, but there may also be an alternative etiology such as the subject's clinical status or underlying factors including other therapy.

Probable: There is a high degree of certainty that a relationship to the investigational product exists. There is a reasonable temporal association, and the event cannot be explained by known characteristics of the subject's clinical state or factors including other therapy.

Definite: An association exists between the receipt of investigational product and the event. An association to other factors has been ruled out.

5.1.4 Serious Adverse Events

An AE or suspected adverse reaction is considered “serious” if, in the view of either the investigator or sponsor, it results in any of the following outcomes:

- Death
- Life-threatening AE. An AE or suspected adverse reaction is considered “life threatening” if, in the view of either the investigator or sponsor, its occurrence places the patient or subject at immediate risk of death. It does not include an AE or suspected adverse reaction that, had it occurred in a more severe form, might have caused death.
- Inpatient hospitalization or prolongation of existing hospitalization
- Persistent or significant incapacity or substantial disruption of the ability to conduct normal life functions
- Congenital anomaly/birth defect
- Important medical events that may not result in death, be life threatening, or require hospitalization may be considered serious when, based upon appropriate medical judgment, they may jeopardize the patient or subject and may require medical or surgical intervention to prevent one of the outcomes listed in this definition. Examples of such medical events include allergic bronchospasm requiring intensive treatment in an emergency room or at home, blood dyscrasias or convulsions that do not result in inpatient hospitalization, or the development of drug dependency or drug abuse.

Hospitalization is to be considered only as an overnight admission. Hospitalization or prolongation of a hospitalization is a criterion for considering an AE to be serious. In the absence of an AE, the participating Investigator should not report hospitalization or prolongation of hospitalization on a form. This is the case for Hospitalization for survey visits or annual physicals.

In addition, a hospitalization planned before the start of the study for a preexisting condition that has not worsened does not constitute an SAE (e.g., elective hospitalization for a total knee replacement due to a preexisting condition of osteoarthritis of the knee that has not worsened during the study).

If there is any doubt whether the information constitutes an AE or SAE, the information is treated as an AE or SAE.

5.1.5 Vital Signs

Vital signs, (minus body temperature), will be continuously monitored for 24 hours post-dosing. For reporting purposes, observations at specific time points as defined in Section 3.2 will be used. Where the time of vital signs monitoring coincides with a blood draw, vital signs will be taken prior to the scheduled blood draw. Vital signs may be taken at other times, if deemed necessary.

5.1.6 Clinical Laboratory Tests

5.1.6.1 Hematology and Coagulation

The following hematological tests will be performed:

- Red Blood Count
- White Blood Count Total
- Hematocrit
- Hemoglobin
- Platelet Count
- Absolute Eosinophil Count
- Absolute Basophil Count
- Absolute Monocyte Count
- Absolute Neutrophil Count
- Mean Corpuscular Volume
- Mean Corpuscular Hemoglobin Concentration
- Mean Corpuscular Hemoglobin
- Absolute Lymphocyte Count
- Red (cell) Distribution Width

The following coagulation tests will be performed:

- Prothrombin Time
- Partial Thromboplastin Time
- Fibrinogen

5.1.6.2 The following serum chemistry tests will be performed:

- Glucose
- Uric Acid
- Blood Urea Nitrogen
- Creatinine
- Creatine kinase
- Sodium
- Potassium
- Chloride
- Calcium

- Phosphorous
- Protein, Total
- Albumin
- Globulin
- Albumin/Globulin Ratio
- Bilirubin, Total
- Bilirubin, Direct
- Alkaline Phosphatase
- Lactic Dehydrogenase
- Aspartate Aminotransferase
- Alanine Aminotransferase
- Gamma Glutamyl Transferase
- Iron
- Total Cholesterol
- Triglycerides
- Magnesium
- Carbon Dioxide

5.1.6.3 The following urinalysis tests will be performed:

- Color
- Appearance
- Specific Gravity
- pH
- Protein
- Glucose
- Ketones
- Occult Blood
- Leukocyte Esterase
- Nitrite
- Bilirubin
- Urobilinogen
- Magnesium (with calculation of fractional excretion)

- Creatinine
- Potassium (with calculation of fractional excretion)

5.1.6.4 Pregnancy Screen

All female participants, regardless of childbearing potential, will undergo 2 pregnancy tests prior to receiving the study drug. A serum pregnancy test to measure human β -chorionic gonadotropin will be administered during screening and also within 24 hours prior to dosing in a controlled environment. A pregnancy test will also be conducted on SD 8, or at study termination, if it occurs before SD 8.

5.1.6.5 Additional Tests

The following tests will be performed:

- Serology (screening only)
 - HIV Test (1 and 2)
 - FTA-ABS Test for Syphilis
 - Hepatitis B Virus Surface Antigen
 - Hepatitis C Virus
- Alcohol Breathalyzer
- Urine Drug Screen (screening, Day -1, Day 8)
 - Barbiturates
 - Benzodiazepines
 - Cannabinoids
 - Cocaine
 - Opiates
 - Methadone
 - Phencyclidine
 - Propoxyphene
 - Oxycodone
 - Tricyclic Antidepressants
 - Amphetamines
 - Methylene dioxyamphetamine

5.1.7 Electrocardiograms

The 3-5-lead ECG will be utilized for continuous monitoring starting at 1 hour prior to dosing and ending at 24 hours post dose.

Due to the continuous monitoring with 3-lead and large number of 12-lead ECGs during the first 24 hours, the ECG electrodes may be left in place from pre dose through 24 hours post dose (and replaced as necessary).

Note: Participants will not be allowed to shower from pre dose until after all 24-hour, post-dose procedures have been completed and the electrodes removed.

5.1.8 Neuropsychiatric/Behavioral Assessments

Assessments of neuropsychiatric/behavioral symptoms will be performed by study staff using the C-SSRS, BPRS (expanded version 4.0, 24 items), and RASS (if general agitation or sedation are reported). A psychiatrist will be available on-site to consult with the investigator throughout the study. At the investigator's request, the psychiatrist will come to the clinic to evaluate a subject.

The C-SSRS Baseline/Screening version will be administered by a physician, physician assistant, or nurse at screening, and the C-SSRS Since Last Visit version will be administered at SD -1 and at follow-up on SD 8. Scoring and analysis will be performed according to the Columbia-Suicide Severity Rating Scale Scoring and Data Analysis Guide. Study staff administering the C-SSRS will complete C-SSRS training. The C-SSRS has excellent inter-rater reliability².

The BPRS will be performed by a psychologist or trained clinician. The BPRS will be assessed at screening, SD -1 (baseline), at 6 (+ 2) hours post dose (timing at the discretion of the investigator or designee), 48 hours post dose (prior to discharge), and on SD 8. In order to improve reliability between administrations, a structured interview guide will be used and the same clinician will administer the BPRS to each participant. For BPRS items assessed over time (e.g., items #1, 2, and 3), the reference period of assessment should be over the prior week, except for assessments performed at 6 and 48 hours post dose, which will be assessed since the prior assessment. The BPRS has low inter-rated reliability, and measures will be taken to ensure that it is captured consistently over time.

5.1.9 Cognitive Assessment

The digit symbol substitution test (DSST) will be used to measure cognitive impairment associated with Scop HBT. Study staff are experienced at performing the test, which typically takes 8 minutes to complete. The DSST will be administered at screening, at SD -1 (baseline), 48 hours after injection (SD 3), and at the SD 8 follow-up visit. The DSST conducted at screening is intended to reduce practice effects. If the PI or designee determines a subject is incapable of engaging in the DSST at one or more time point(s), the reason(s) why the DSST assessment(s) could not be done will be documented by time point in the source documentation.

The DSST will be used test for persistent cognitive impairment associated with Scop HBT at the individual and population levels. Differences in raw scores (number of correct pairings in 120 seconds) between baseline and SD 3 and SD 8 will be presented individually in listings. The

² Posner K, Brown GK, Stanley B, Brent DA, Yershova KV, Oquendo MA, Currier GW, Melvin GA, Greenhill L, Shen S, Mann JJ (2011). *The Columbia-Suicide Severity Rating Scale: Initial Validity and Internal Consistency Findings from Three Multisite Studies with Adolescents and Adults*. American Journal of Psychiatry 168(12): 1266-77.

persistent effects of Scop HBT on cognition will also be assessed through comparison of within-person changes in scores from baseline between active and placebo groups

5.1.10 Injection Site Assessments

At approximately 5 minutes after injection, the subject will be asked by the study staff to rate the maximum intensity of pain, pruritus, tingling, and numbness at the injection site using the VAS (*see protocol* Appendix A). The VAS will also be completed at pre dose and at 10, 15, 30, and 45 minutes and 1, 1.5, 3, 5, 8, 12, 24, and 48 hours post dose, and at Day 8. In addition, an injection site assessment for presence and severity of pain, tenderness, erythema, and induration/swelling will be performed by a physician, physician assistant, or nurse approximately 5 minutes after injection and for all subsequent time points (as stated above; *see protocol* Appendix C). Refer to *protocol* Appendix B for the Toxicity Grading Scale for Injection Site Reactions.

The anticipated neuropsychiatric effects of Scop HBT may hinder obtaining reasonable subjective data on the VAS, especially at the earlier post-dose time points. If the PI or designee determines a subject is incapable of providing valid responses at one or more time point(s), the reason(s) why the VAS assessment(s) could not be done will be documented by time point in the source documentation.

5.1.11 Physical Examinations

Each subject will have a complete physical examination at screening, Day -1, pre-injection (abbreviated) and at 48 hours (abbreviated) and SD 8 post-injection. A complete physical examination will include the assessment of the following body systems: general appearance, eyes, ears, nose and throat, chest/abdominal, heart/cardiovascular, abdomen/gastrointestinal, lymph nodes/spleen, genitourinary, musculoskeletal, skin, neurological, hepatic and other. The results of the physical examination will be recorded in the subject's medical record and clinically significant findings will be recorded in the case report form (CRF). The abbreviated physical examination will include documentation of any changes from the screening assessment.

5.2 PHARMACOKINETICS ENDPOINTS

Determination of PK parameters at varying dose levels is an objective of this study, as is investigation of dose proportionality for C_{max} and AUC_{∞} . The PK measures, their definitions, methods of calculation, and methods for their statistical interpretation are described further.

5.2.1 Plasma Pharmacokinetics

The PK parameters will not be calculated as part of this SAP, but they will undergo statistical analysis according to this SAP. The PK parameters will be calculated by the Battelle Chemistry Technical Center according to their Standard Operating Procedures and conventions, using WinNonlin Phoenix v8.1). Plasma concentration time profiles for each subject tested will be evaluated using semi-log plots and characterized using noncompartmental analysis.

Descriptive statistics for the concentration of Scopolamine in plasma and for the PK parameters will be calculated at each scheduled time point. The summary of descriptive statistics at each time point will be displayed by cohort and dose level. The statistics will include sample size, mean, median, standard deviation (SD), standard error of the mean (SEM), percent coefficient of variance (CV), minimum, and maximum for continuous variables, and 95% confidence intervals. Additionally, geometric means will be calculated for AUC_{∞} and C_{max} .

Analysis of plasma concentrations will be performed for each subject on samples collected prior to dosing and at the following post-dose target time points: 2, 5, 10, 15, 20, and 30 minutes and 1, 2, 4, 8, 12, 24, 36, and 48 hours post dose. Table 6 describes the time windows for blood draw. PK parameters will be calculated using the time points of the actual blood draw, rather than the target time. The serum PK parameters that will be analyzed are listed below and are outlined and defined as in the protocol:

- **C_{max}** : Maximum measured plasma concentration over the time span specified.
- **T_{max}** : Time of maximum measured plasma concentration. If the maximum value occurs at more than one time point, T_{max} is defined as the first time point with this value.
- **$t_{1/2}$** : Apparent first-order terminal elimination half-life will be calculated as $0.693/k_e$.
- **V_d/F** : Apparent Volume of distribution.
- **Cl/F** : Apparent Volume of blood or plasma cleared of drug per unit time.
- **MRT (Mean Residence Time)**: Mean time the drug spends in the body before being eliminated.
- **AUC_{last}** : The area under the plasma concentration versus time curve, from time 0 to the last measurable concentration, as calculated by the linear trapezoidal method.
- **AUC_{∞}** : The area under the plasma concentration versus time curve from time 0 to infinity. AUC_{∞} is calculated as the sum of AUC_{last} plus the ratio of the last measurable plasma concentration to the elimination rate constant (k_e). The elimination rate constant will be determined from the terminal linear phase of the plasma concentration time profile.
- **$C_{max}/Dose$** : Dose normalization of C_{max} for evaluation of dose proportionality.
- **$AUC_{\infty}/Dose$** : Dose normalization of AUC_{∞} for evaluation of dose proportionality.

The terminal elimination phase is used to estimate a number of PK parameters. No value for V_d/F , Cl/F , AUC_{∞} , or $t_{1/2}$ will be reported for cases that do not exhibit a terminal log-linear phase in the concentration versus time profile. The PK analyses will not include the placebo group.

Outlier screens will first be carried out. For each PK parameter a one-way, heterogeneous variance analysis will be carried out across dose groups. Studentized residuals (i.e. residuals divided by their standard errors) will be calculated within each group and combined across groups. Studentized residuals in excess of three in absolute value will be considered “tentative outliers”. The tentative outliers will be examined by Battelle to determine if they are due to testing errors or data entry errors. If so, they will be reported and omitted from subsequent analyses. If the tentative outliers are correctly determined they will be treated as outliers and subsequent analyses will be carried out both including and excluding the outlying values.

Table 6: Pharmacokinetic Blood Sample Deviation Windows

Target Time Point	Acceptable Sample Collection Time Point Range		
	Low-End Range	High-End Range	Window
2 min	1 min 50 s	2 min 10 s	20 seconds
5 min	4 min 40 s	5 min 20 s	40 seconds
10 min	9 min 30 s	10 min 30 s	60 seconds
15 min	14 min 15 s	15 min 45 s	60 seconds
20 min	19 min	21 min	2 minutes
30 min	28.5 min	31.5 min	3 minutes
1 h (60 min)	57 min	63 min	6 minutes
2 h (120 min)	114 min	126 min	12 minutes
4 h (240 min)	228 min	252 min	24 minutes
8 h (480 min)	465 min	495 min	30 minutes
12 h (720 min)	705 min	735 min	30 minutes
24 h (1440 min)	1425 min	1455 min	30 minutes
36 h (2160 min)	2145 min	2175 min	30 minutes
48 h (2880 min)	2865 min	2895 min	30 minutes

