10. PHARMACOKINETIC SAMPLE COLLECTION

Blood samples (approximately 10 mL each draw) will be obtained for PK assessments within 2 hours prior to dosing and at 2, 5, 10, 15, 20, and 30 minutes and 1, 2, 4, 8, 12, 24, 36, and 48 hours post dose. These sampling points should allow for adequate and full characterization of the Scopolamine HBT PK profile.

Scopolamine HBT PK assessments will include determination of the following parameters: observed C_{max} and T_{max} , V_d/F , $t_{1/2}$, Cl/F , AUC_{last} , AUC_{∞} , $C_{max}/Dose$, MRT, and $AUC_{\infty}/Dose$. Samples will be analyzed for Scopolamine HBT at Battelle in Columbus, Ohio, using a high-performance liquid chromatography-tandem mass spectrometry method validated with respect to accuracy, precision, linearity, sensitivity, and specificity. Samples will be shipped as agreed upon by the site and Battelle. It is expected that plasma samples will be analyzed and concentration time profiles constructed for each cohort to assist the DSMB in making dose-escalation recommendations. After analysis, samples will be stored until study report approval and permission from the sponsor has been received to dispose or ship the samples to a sponsor-designated location.

The backup (“B”) PK samples will be stored at the investigator site at -20°C or lower until directed to ship by Battelle. These samples will be shipped to Battelle’s Chemistry Technical Center in Columbus, Ohio, for confirmatory testing, if applicable. Approximately 2 mL of plasma for each PK assessment will be transferred to a long-term storage facility where samples will be stored at -20°C or lower for at least 2 years after FDA approval of the last indication for this product. These backup samples may be used for additional or repeat PK testing, as required.

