13.1. Accounting for Missing, Unused, and Spurious Data

Instances of missing data will be reported along with a reason that data is missing. If multiple measurements are collected, a reason for repeat measurement will be recorded, and the data point corresponding to erroneous or incomplete data collection will be censored. Otherwise, all data will be included in the analysis as specified in the SAP. Data collected following administration of rescue medication will be censored in the analysis of endpoints that are likely to be affected by the rescue medications (BPRS, RASS, DSST, C-SSRS). However, injection site VAS scores will not be censored following administration of rescue medications.

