3.4 STUDY POPULATION

[figure not shown]
The study will include up to 60 male and female volunteers, 18 to 55 years of age, who will be enrolled in 5 dosing groups (cohorts) of 8 to 12 participants each. The actual number enrolled in the study will be determined by the safety responses noted during the study. Each of the 5 cohorts will include at least 3 male and 3 female participants enrolled among the first 8 participants in the cohort to ensure that at least 1 male and 1 female subject in each dosing group receive active drug. Each cohort will include 6 to 9 individuals receiving active and 2-3 receiving placebo doses (total of 30-45 active and 10-15 placebo).

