6.4 UPPER-BOUND ESTIMATION FOR DLTs & SAEs

As part of the first objective, to characterize the safety and tolerability of Scop HBT IM injection at varying dosages, upper limits for the probability of an event at each dosage will be estimated using data on the occurrence of extreme DLTs, non-extreme DLTs, and SAE.

Dose progression follows rules that require dosing be halted if an extreme DLT or a SAE related to the drug occurs within any cohort. Therefore, the maximum number of extreme DLTs that can occur in a cohort prior to stopping is one. Should one nonextreme DLT occur in the first four participants or two in the first 8 participants, dosing will be halted. If dosing is resumed (upon determination of the PI, DSMB, and sponsor) and a second nonextreme DLT occurs among the first 4 in cohort or 3 total DLTs occur, dosing and enrollment will be halted.

Confidence intervals will be determined using 80% confidence interval, such that there is a 10% probability that the true value exceeds the upper-bound. The Pearson-Clopper interval is the most conservative among the binomial intervals, resulting in the highest upper confidence bounds.

Should no events of any type occur within a cohort, with 6 participants dosed, the 80% confidence interval upper bound for the probability of any event is 0.32. Should one extreme

DLT or SAE occur in any cohort, the upper bound for the SAE/extreme DLT will depend on the number dosed prior to the event occurring. Table 8 shows the upper bounds of confidence intervals based on the number of participants receiving active Scop HBT.

Table 8: Upper-bound estimates of Risk Inferred from Events in Cohort

		Number Receiving Active Scop HBT			
		2	4	6	9 ¹
Event Type	Number of Participants with Event	80% C.I. Upper Bound (Pearson-Clopper Method)			
No Events	0	N/A	N/A	0.32	N/A
Extreme DLT	1	0.95	0.68	0.51	0.37
Nonextreme DLT	1 of first 4 in a cohort, none thereafter	0.95	0.68	0.51	0.37
	2 in the first 8 in a cohort	1.0	0.86	0.67	N/A
	2 of the first 4 in a cohort	1.0	0.86	N/A	N/A
	3 in any cohort	N/A	0.97	0.80	0.60
SAE not already designated as a DLT (except unrelated)	1	1.0	0.68	0.51	0.37

¹If nonextreme DLT occurs in a given cohort, the cohort may be expanded to 12 participants, a maximum of 9 of whom will receive active Scop HBT.

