6.15 PHARMACOKINETIC ANALYSES

6.15.1 Plasma Pharmacokinetics

The estimation of pharmacokinetic parameters of interest is not described within this SAP. A separate PK report will detail methods and limitations of the estimation of PK parameters. However, PK parameters will be analyzed as part of this SAP.

PK parameters will be assessed for homoskedasticity prior to modeling using ANOVA. For parameters that vary by orders of magnitude across dose groups, a logarithmic transformation will be carried out prior to testing for homogeneity of variance. Otherwise a likelihood ratio test for homogeneity of variance will be carried out on the untransformed PK values or on transformed values, as appropriate. The tests for homogeneity of variance will exclude outlying values. If there are significant differences ($p < 0.05$) in variances across dose groups, comparison of PK means across dose groups will be carried out based on a heterogeneous variance analysis of variance. Otherwise it will be carried out based on a homogeneous variance analysis of variance.

Dose-equivalency of five PK parameters (T_{max} , $t_{1/2}$, V_d/F , CL_F , MRT) will be tested using ANOVA. Models will adjust for sex of the subject. Equation 3 presents the model to be used for all ANOVA of PK parameters,

$$G(Y_i) = \beta_0 + \beta_1 \times I(D_i = 2) + \beta_2 \times I(D_i = 3) + \beta_3 \times I(D_i = 4) + \beta_4 \times I(D_i = 5) + \beta_5 \times Sex_i + \varepsilon_i \quad (8)$$

, where G is a link function (or identity), Y_i is the PK parameter of interest i , β_0 is the change in PK parameter for the placebo group, D_i is the dosage level ($1=0.005$, $2=0.007$, $3=0.011$, $4=0.014$, $5=0.021$ mg/kg), and ε_i is an error term each for participant i . Models will control for the sex of the participant. The significance of the difference in parameters by dose level will be tested using a likelihood ratio test for the joint null hypothesis: $H_0: \beta_1 = \beta_2 = \beta_3 = \beta_4 = 0$. If bootstrapping is used, a null distribution will be generated using an F-statistic, as described previously. For parameters where dose-proportionality is assessed, the equivalency of each parameter with the next higher dose level will be tested, using the null hypotheses:

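### The PK outlier screen in SAP 5.2.1 cannot flag any value: with 6 to 9 active subjects per dose its residual is capped at 2.24 to 2.83, below the cut-off of 3

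*SAP*

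**What the plan says.** SAP 5.2.1 (Plasma Pharmacokinetics) begins the PK analysis with an outlier screen. For each parameter it fits a one-way model across dose groups with heterogeneous variances. It defines the studentized residual itself: "i.e. residuals divided by their standard errors) will be calculated within each group and combined across groups". The trigger is "Studentized residuals in excess of three in absolute value will be considered" tentative outliers.

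Three actions depend on that flag:

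- The laboratory examines the value for testing or data entry errors. Confirmed errors are reported and dropped (SAP 5.2.1).
- If the value is correct, "subsequent analyses will be carried out both including and excluding the outlying values" (SAP 5.2.1).
- "The tests for homogeneity of variance will exclude outlying values" (SAP 6.15.1).

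Group size is fixed elsewhere. SAP 3.4 says "Each cohort will include 6 to 9 individuals receiving active and 2-3 receiving placebo doses", and the footnote to Table 8 in SAP 6.4 gives "a maximum of 9 of whom will receive active Scop HBT" after expansion. Placebo subjects are left out of the PK analyses (SAP 5.2.1), and dosed subjects are not replaced (SAP 6.12.1). The screen therefore works on 6 to 9 values per dose, or fewer when a profile lacks a terminal log-linear phase.

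**The concern.** When a residual is scaled by its own group's standard deviation, an extreme value inflates the denominator along with the numerator. In small groups this puts a hard ceiling on the ratio. If the ceiling lies below the cut-off, the screen is inert.

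What is at stake is the automatic trigger and the pre-specified sensitivity analysis. A report that no outliers were identified would be guaranteed by arithmetic, yet would read as evidence of clean data. Characterizing PK and assessing dose proportionality of Cmax and AUC to infinity is a study objective (SAP 2), and it rests on 6 to 9 subjects per dose.

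**Working it through.** The SAP gives no derivation of the cut-off of 3, so there is no plan figure to reproduce. The check is whether 3 can be exceeded.

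**Ceiling.** Let e be one residual in a group of n values, and s the group SD on n-1 degrees of freedom. The standard error of the residual is s·sqrt(1-1/n). The other n-1 residuals sum to -e, so their squares sum to at least e²/(n-1). Hence

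(n-1)s² ≥ e² + e²/(n-1) = e²·n/(n-1), so s² ≥ e²·n/(n-1)².

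Then r² = e² / [s²(1-1/n)] ≤ [(n-1)²/n]·[n/(n-1)] = n-1, so |r| ≤ sqrt(n-1).

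The size of the outlier cancels. The bound holds for any distribution and after any transformation. Combining residuals across groups does not lift it, because each is already scaled by its own group's SD.

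| Active n in dose group | sqrt(n-1), SAP definition | sqrt(n), maximum-likelihood variance |
|---|---|---|
| 6 | 2.24 | 2.45 |
| 7 | 2.45 | 2.65 |
| 8 | 2.65 | 2.83 |
| 9 | 2.83 | 3.00 |
| 10 | 3.00 | 3.16 |
| 11 | 3.16 | 3.32 |

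Under the SAP's definition at least 11 active subjects at one dose are needed. With a maximum-likelihood variance the ceiling reaches 3 at n=9 but does not exceed it.

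**Simulation.** In 400,000 groups each from normal, lognormal and Cauchy distributions, at n=6 and n=9, no residual exceeded 3. A planted 1000-fold error scored 2.236 (n=6) and 2.828 (n=9).

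**What a missed error would do.** Suppose one parameter value is wrong by a factor of 10 and every other review misses it. That dose's expected arithmetic mean is multiplied by 1 + 9/n = 2.5 (n=6) or 2.0 (n=9), and its geometric mean by 10^(1/n) = 1.47 or 1.29. A 3-fold error gives 1 + 2/n = 1.33 or 1.22, and 3^(1/n) = 1.20 or 1.13.

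**Reachable alternatives.** Simulated with five doses and lognormal data, screened on the log scale. The CVs are assumptions, since the documents give none.

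| | Option A: SAP model, cut-off 2.09 (n=6) or 2.36 (n=9) | Option B: pooled variance, leave-one-out, cut-off 3 |
|---|---|---|
| At least one false flag per parameter, equal variances | about 17-21% | 18-21% |
| Same, one dose at CV 80% and the rest 40% | about 17-21% | 41-50% |
| 10-fold error flagged, CV 40% | 61-89% | about 99% |
| 10-fold error flagged, CV 60% | 30-52% | 77-81% |
| 10-fold error flagged, CV 80% | 17-30% | 50-55% |

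**Study-wide false flags.** Nine positive continuous parameters would be screened. On the log scale AUC to infinity, its dose-normalized form and Cl/F give the same residuals up to sign, as do Cmax and Cmax/Dose, if dose is taken per kg. About six distinct screens remain. For Option B, assumed correlations of 0 to 0.8 between them give a 55-74% chance of at least one false flag in a clean study. For Option A, if the six were independent, 1 - 0.83^6 = 67% and 1 - 0.79^6 = 76%; correlation would lower this.

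**The case against.** **Studentized might mean leave-one-out.** Leave-one-out residuals have no ceiling. But the SAP's own parenthetical defines the residual otherwise. Within-group leave-one-out at 3 would also flag at least one correct value in about 63-75% of clean datasets per parameter. Either reading needs an edit.

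**Other checks would catch a gross error.** Much of this stands. SAP 6.10 requires a Shapiro-Wilk test and quantile-quantile plots of the ANOVA residuals. With one 10-fold error among 30 or 45 values, a log-scale Shapiro-Wilk test at 0.05 rejects 87-92% of the time at CV 40%, 43-47% at 60% and 21-23% at 80%, and the plot is inspected as well. SAP 5.2.1 also provides semi-log profiles and reports minimum, maximum and CV by dose. The protocol adds listings (12.1.1), PK review at the end of each cohort (7.6.2) and spare aliquots: "These backup samples may be used for additional or repeat PK testing, as required". None of these starts the laboratory check or the with/without analysis. Protocol 13.1 censors an erroneous point when a measurement was repeated; beyond that, "Otherwise, all data will be included in the analysis as specified in the SAP".

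**The laboratory may have its own trigger.** It calculates the parameters under its own procedures, and a separate PK manual and report govern methods and limitations (SAP 4.3, 5.2.1). These are not in view. What is established is that the SAP 5.2.1 trigger cannot fire, not that no check will take place.

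**The size is an upper-end scenario.** This stands. A 10-fold assay error in one sample can pass straight to Cmax, but AUC, MRT, Cl/F and Vd/F draw on up to 14 post-dose samples and would generally move less.

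**Conclusion.** The point holds as a matter of algebra. Under the SAP's definition and planned group sizes the screen has zero probability of flagging a value. The three actions tied to it are never triggered by this rule. The result needs no assumption about variability or distribution. It would change only with 11 or more active subjects at one dose, which is outside the plan, or with a different residual from the one the SAP defines.

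A reader might infer that the dose-proportionality tests are invalid or their error rates inflated. The documents do not support that: a screen that never fires simply leaves all values in, and SAP 6.1 says the objectives are addressed mainly through descriptive statistics. A reader might also infer that gross errors will go unnoticed. That does not follow either, given the remaining diagnostics and reviews. The loss is limited to the automatic trigger and the pre-specified sensitivity analysis.

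The detection and false-flag figures for the alternatives rest on assumed lognormality, CVs of 40-80% and, study-wide, assumed correlations of 0 to 0.8.

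**What to change.** Before unblinding, replace the rule in SAP 5.2.1 with one that can be reached. After unblinding, SAP 6.2 would make a new screen post hoc. Apply it on the log scale to Cmax, both AUCs, the dose-normalized forms, half-life, Vd/F, Cl/F and MRT. SAP 6.10 already notes that lognormality is commonly assumed for PK parameters. Review Tmax by listing only, since it can fall only at or near the scheduled draws. Keep the laboratory check and the with/without analyses as they are.

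- **Option A** keeps the heterogeneous-variance model and lowers the cut-off to about 2.09 at n=6 and 2.36 at n=9, with values for other n derived the same way. False flags stay stable when variances differ, but detection is lower.
- **Option B** uses externally studentized residuals from a pooled-variance model with cut-off 3. Detection is better, but false flags rise to 41-50% per parameter when one dose is more variable, and 91-94% of them fall in that dose. If B is chosen, SAP 6.15.1 should state that flagged values confirmed correct stay in the variance-homogeneity test; otherwise the screen would remove the very spread that test is meant to detect. The log scale is essential: on raw lognormal data the same rule gives 46-85% false flags.

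The edit is two or three sentences in 5.2.1, plus one clause in 6.15.1 under Option B. The running cost is false flags: 55-74% for at least one in a clean study under Option B, and of similar order under Option A. Each costs a laboratory check and a duplicate analysis. The SAP should state that cost alongside the rule.
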